7.5. ANTICOAGULATION / DUAL ANTIPLATELET DISCONTINUATION (OR PLANNING) VISIT

This visit may be done by the subject's primary care physician as part of the standard of care for the subject. If done at a location other than the research location, the documentation of the visit will need to be obtained, reviewed by the site PI, and filed in the subject's research records. The visit details may then be entered in the EDC

system and made available for monitoring/source data review. Any part of the evaluation not completed will be considered a protocol deviation.

For subjects discharged with anticoagulation or dual antiplatelet therapy, (see Appendix 4 for American College of Cardiology guidelines for anticoagulation therapy¹¹) an additional visit shall be performed to assess the possibility to stop the anticoagulation or antiplatelet therapy and plan the CT scan. The discontinuation of anticoagulation or antiplatelet therapy is usually around 3 months after surgery in subjects without a further clinical need for this treatment. This additional visit shall evaluate the following information:

- Subject status
- Physical evaluation (including cardiac rhythm and NYHA functional classification)
- Medications
- SAEs

Subjects which are not able to come off ACT/DAPT treatment will remain in the study and followed through the 1-year evaluation.

7.6. 1ST CT SCAN VISIT (1 TO 6 MONTHS FOLLOW-UP VISIT)

This visit is intended to be done a minimum of 30-days after the initial discontinuation of anti-coagulation or dual antiplatelet therapy; usually between 1-6 months postimplant, or at least one month after discharge for subjects discharged without anti-coagulation therapy. Follow-up evaluations are to be conducted in an office, hospital or clinic setting and are to be performed by the PI or his/her designee.

The following data listed below shall be collected:

- Subject status
- Physical evaluation (including cardiac rhythm and NYHA functional classification)
- Medications
- Hemodynamic data from TTE examination measured at investigational site (MPG; PPG, EOA, aortic regurgitation with severity and location)
- CT Scan

- TEE only in subjects that are unable to undergo CT scan at the time of followup
- Medications
- SAEs

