2.3 SAMPLE SIZE CALCULATION

A sufficient number of subjects will be enrolled in this study to allow a minimum of 75 evaluable CT scans for the primary endpoint. Evaluable scans are those where a determination of normal or abnormal leaflet motion is possible. Considering an attrition rate of 15% of subjects, the sample size targeted for enrollment is approximately 88 subjects.

A sample size of 75 evaluable CT scans produces an Exact two-sided 90% CI with a width lower than 13% when the sample proportion is lower than 10% (evaluation calculated using PASS software, version 13).

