5.1 GENERAL PRINCIPLES

The statistical analysis will be performed on the analysis study database with SAS version 9.4 or above (SAS Institute, Cary, N.C.).

If two or more of the analysis sets as defined in Section 6 coincide or the difference is less than 5%, presentations will only be prepared for the population less restrictive.

The default significant level will be 10%. Confidence Intervals (CIs) will be calculated at 90% confidence level and all tests will be two-sided, unless otherwise specified in the description of the analyses.

All the data collected and derived in the study will be presented in subject data listings.

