5.3 SUBGROUPS DEFINITIONS

The following subgroups will be defined:

- Concomitant Procedures (at implant):
 - Subject implanted with a concomitant procedure performed.
 - Subject implanted without a concomitant procedure performed.
- Subject symptoms (at first/second CT scan, as appropriate):
 - Asymptomatic
 - Symptomatic
- ACT/DATP (at hospital discharge):

COPYRIGHT LIVANOVA. ALL RIGHTS RESERVED. MAY NOT BE REPRODUCED WITHOUT PERMISSION. ALL HARD COPIES SHOULD BE CHECKED AGAINST THE CURRENT ELECTRONIC VERSION WITHIN MASTERCONTROL PRIOR TO USE AND DESTROYED PROMPTLY THEREAFTER. ALL HARD COPIES ARE CONSIDERED UNCONTROLLED DOCUMENTS.

LN-GLB-CLN-TEM-0033 rev1 Page 9 of 42

- Subject on ACT/DAPT at hospital discharge (or 30-days after implant)
- Subject off ACT/DAPT at hospital discharge (or 30-days after implant)
- Core Lab evaluation (at first/second CT scan, as appropriate) by:
 - o CT scan
 - Transesophageal Echocardiogram (TEE)

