11.5 Freedom from Valve Safety

The following mortality and morbidity outcomes will be analyzed by means of time to event methods:

all-cause mortality

COPYRIGHT LIVANOVA. ALL RIGHTS RESERVED. MAY NOT BE REPRODUCED WITHOUT PERMISSION. ALL HARD COPIES SHOULD BE CHECKED AGAINST THE CURRENT ELECTRONIC VERSION WITHIN MASTERCONTROL PRIOR TO USE AND DESTROYED PROMPTLY THEREAFTER. ALL HARD COPIES ARE CONSIDERED UNCONTROLLED DOCUMENTS.

LN-GLB-CLN-TEM-0033 rev1 Page 21 of 42

- valve re-intervention
- myocardial infarction
- structural valve deterioration
- moderate or severe valve regurgitation
- valve endocarditis
- valve thrombosis
- thromboembolic events
- hemolysis
- major bleeding
- pacemaker implantation

Cox's proportional hazards regression models (Cox 1972, Breslow 1975) will be performed including, one by one, the following covariates: age class [refers to "≥18 and <65" years], gender [refers to "male"], ethnicity [refers to "not Hispanic or Latino"], presence of subject risk factor at baseline [refers to "No"], , NYHA at baseline [refers to "Class I"], abnormality of ascending aorta or of aortic root at implant [refers to "No"], presence of aortic regurgitation measured by post-implant intraoperative TEE [refers to "No"], reduced leaflet motion at first CT scan [refers to "No"], including the subgroup defined in Section 5.3: concomitant procedures [refers to "without"], subject symptoms [refers to "asymptomatic"], ACT/DATP [refers to "off"], Core Lab evaluation [refers to "TEE"].

Study: APR002 BELIEVE

Hazard rate, and its 90% CI, will be reported for each covariate.

Proportional hazard assumption will be investigated for each time-dependent outcome. In case of non-proportional hazards, a Weibull model will be assumed as parametric form of the distribution of survival times.

An additional analysis will be performed in order to evaluate the time free from ACT/DAPT to primary endpoint (reduced leaflet motion) up 1 year post-implant. Kaplan-Meier estimates and plots of time to event after implant will be produced as in Section 5.2. Subjects will be included in the analysis starting from their stop date of ACT/DAPT until the first evaluation of leaflet motion.

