ENR population	 SCR flag= "Yes" and DXSTDAT2 not missing ("Implant Surgical Details" e-CRF) and existing Enrolled Date
SAF population	 ENR flag= "Yes", and DXPERF= "Yes" ("Implant Surgical Details" e-CRF)
PP population	As reported in the Believe Risk Based Study Management Plan.
Time to study	"Implant Surgical Details" e-CRF and "Study Termination" e-CRF
termination (months)	[DSSTDAT – DXSTDAT2 + 1] / 30.4375

COPYRIGHT LIVANOVA. ALL RIGHTS RESERVED. MAY NOT BE REPRODUCED WITHOUT PERMISSION. ALL HARD COPIES SHOULD BE CHECKED AGAINST THE CURRENT ELECTRONIC VERSION WITHIN MASTERCONTROL PRIOR TO USE AND DESTROYED PROMPTLY THEREAFTER. ALL HARD COPIES ARE CONSIDERED UNCONTROLLED DOCUMENTS.

LN-GLB-CLN-TEM-0033 rev1 Page 40 of 42

Time to event	"Implant Surgical Details" e-CRF
(months)	[Even date – DXSTDAT2 + 1] / 30.4375 Subjects ongoing and who are free from event at the analysis cutoff date will be censored at the analysis cut-off date. Subjects who have discontinued without an event will be censored at the date of discontinuation.
Age at Enrollment (years)	"Demographics" e-CRF and "Inclusion/Exclusion Criteria" e-CRF Age= [ICFDAT - BRTHDAT + 1]/365.25 As only month and year of birth are reported in the CRF, 1 st day of the month will be used for birth date.
Change from baseline	Test Value at Visit X - Baseline Value

Where

ACTDIDAT = "Date Subject Discontinued ACT/DAPT Therapy"

BRTHDAT= "Date of Birth"

CPAETERM= "Complications/Please specify if any of the following intraoperative complications occurred. /AE Term"

CPYN= "Was concomitant procedure performed?"

DIMODEL= "Valve Model"

DSDECOD= "Reason for Termination"

DSSTDAT= "Date of Study Termination"

DVDECOD= "Deviation Description"

DVICSPEC= "If Informed Consent, specify reason"

DXPERF= "Was the implant successful?"

DXSTDAT2 = "Date of Implant"

ICFDAT = "Informed Consent Date"

IEYN= "Met All Eligibility Criteria?"

COPYRIGHT LIVANOVA. ALL RIGHTS RESERVED. MAY NOT BE REPRODUCED WITHOUT PERMISSION. ALL HARD COPIES SHOULD BE CHECKED AGAINST THE CURRENT ELECTRONIC VERSION WITHIN MASTERCONTROL PRIOR TO USE AND DESTROYED PROMPTLY THEREAFTER. ALL HARD COPIES ARE CONSIDERED UNCONTROLLED DOCUMENTS.

LN-GLB-CLN-TEM-0033 rev1 Page 41 of 42

IMGTYPE= "Specify the imaging modality currently being used for the subject"

MHCVDAT = "If Myocardial Infarction, date"

MHSTDAT3= "If Stroke, date"

NY= "No/Yes"

SCDISCYN= "Was the subject discharged on anticoagulant and/or dual platelet therapy?"

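### The valve-safety Cox models start at implant but use ACT/DAPT status fixed at discharge, so the hazard ratio includes events that precede the covariate and cannot be read as a therapy effect

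*SAP*

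**What the plan says.** SAP 11.5 lists eleven mortality and morbidity outcomes, among them major bleeding and thromboembolic events. Cox models "will be performed including, one by one, the following covariates", and ACT/DAPT (reference: off) is one of twelve. Each hazard ratio is reported with a 90% interval.

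SAP 5.3 defines the on group as "Subject on ACT/DAPT at hospital discharge (or 30-days after implant"), and SAP 18.13 derives it from the single item SCDISCYN. SAP 18.13 also counts time to event from the implant date. SAP 18.6 allows the discharge visit up to day 30.

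Protocol 7.5 states: "The discontinuation of anticoagulation or antiplatelet therapy is usually around 3 months after surgery" in subjects with no further clinical need. Protocol 6.3.3 excludes conditions requiring long-term therapy. The stop date is collected (ACTDIDAT, "Date Subject Discontinued ACT/DAPT Therapy"). The last paragraph of SAP 11.5 starts a different analysis from the date therapy stopped, but the Cox models do not use that date. If hazards are non-proportional, SAP 11.5 switches to a Weibull model.

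**The concern.** A Cox covariate that does not change over time should be known when the clock starts. This one is not, which raises two separate problems.

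- **Events before the covariate exists.** A bleed on day 3 is counted against a status recorded later. If that bleed influenced the status, the model attributes the cause to its own consequence. A subject who dies in hospital has no natural value. SAP 11.5 gives no rule for such subjects. The general rule in SAP 18.5, under which missing values are not imputed, would remove them if the item is left blank; if it is entered as No, they would be counted as off.
- **Exposure after therapy stops.** Subjects in the on group keep that label to 1 year, although most are expected to stop at about 3 months.

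At stake is a reported hazard ratio for on versus off ACT/DAPT on bleeding and embolism, which readers are likely to take as the effect of therapy.

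**Working it through.** **1. The plan's own figures.** The documents give no event count, power or hazard ratio for these models. The only design figures concern the scan proportion. The widest exact 90% interval below 10% is at 7/75 (9.3%): 4.46% to 16.82%, width 12.35%, which is under the stated 13%. SAP 2.3 adds: "Considering an attrition rate of 15% of subjects, the sample size targeted for enrollment is approximately 88 subjects"; 75/0.85 = 88.2. Both reproduce. They matter here only because they put the number of subjects at about 88.

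**2. Order of events, from the documents.** Day 0: implant, clock starts. Up to day 30: discharge, covariate recorded. About 3 months: therapy usually stops. Day 365: end of follow-up. The model has no landmark, delayed entry or time-updated exposure.

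**3. Dilution with no in-hospital events.** Assumed: discharge day 7, stop day 90, constant background hazard, true on-therapy ratio 3. Follow-up after discharge is 365 − 7 = 358 days, of which 90 − 7 = 83 are on therapy and 275 off (275/358 = 77%). With rare events the fixed covariate estimates

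(83 × 3 + 275 × 1)/358 = 524/358 = 1.46.

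Stop at day 30: (23 × 3 + 335)/358 = 1.13. Stop at day 180: (173 × 3 + 185)/358 = 1.97.

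**4. Adding in-hospital bleeds.** Further assumptions: 75% discharged on therapy, off-therapy bleeding 2% per year, a proportion p bleeding in hospital, and a proportion q of those discharged on therapy.

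- Later risk, on: 1 − exp[−(0.06 × 83 + 0.02 × 275)/365] = 0.0283
- Later risk, off: 1 − exp[−0.02 × 358/365] = 0.0194
- Risk in the on group: [pq + (1 − p) × 0.75 × 0.0283]/[pq + (1 − p) × 0.75]. The off group is analogous, with 1 − q, 0.25 and 0.0194.

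| p | q | Risk ratio, on/off |
|---|---|---|
| 3% | 0.75 (no influence on status) | 1.18 |
| 3% | 0.5 | 4.8%/7.7% = 0.63 |
| 3% | 0.3 | 4.0%/9.8% = 0.41 |
| 1% | 0.75 (no influence on status) | 1.30 |
| 1% | 0.5 | 0.90 |
| 1% | 0.3 | 0.69 |

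Reversal appears only in the rows where the bleed changes discharge status.

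**5. The bias has no fixed direction.** A second set of assumptions has 50% on therapy without an in-hospital event, the same days, and a share F of events before discharge. Then

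HR = [F × q/0.5 + (1 − F) × A]/[F × (1 − q)/0.5 + (1 − F)], with A = (83 × true HR + 275)/358.

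| True HR | F | q | Planned model gives |
|---|---|---|---|
| 2.0 | 0 | – | 1.23 |
| 2.0 | 0.3 | 0.2 | 0.83 (reversed) |
| 0.5 | 0.3 | 0.8 | 1.34 (reversed) |
| 2.0 | 0.6 | 0.8 | 2.27 (inflated) |
| 1.0 | 0.3 | 0.8 | 1.44 (spurious) |
| 1.0 | 0.3 | 0.2 | 0.69 (spurious) |

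Cox fits to 60,000 simulated subjects per scenario agreed where run (for example 1.22, 0.86, 1.39, 1.44 and 0.67 for rows 1, 2, 3, 5 and 6).

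**6. What moving the origin does.** In the same simulations, starting at discharge with the covariate still fixed gave 1.02 and 0.97 for a true 1.0, so the spurious association disappears. For a true 2.0 it gave 1.15 to 1.30, so the dilution remains. Adding time-updated exposure gave 1.72 to 2.27 for a true 2.0, that is, the true value with Monte Carlo scatter.

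**7. Precision at 88 subjects, assumptions of step 4 with p = 3%.** In-hospital bleeds: 88 × 0.03 = 2.6. Later bleeds: 88 × 0.97 × (0.75 × 0.0283 + 0.25 × 0.0194) = 2.2. Total about 4.9, of which 54% come before discharge. With a 75:25 split the ratio of upper to lower 90% limit is exp[2 × 1.645/√(4.9 × 0.1875)], about 31. Bleeds expected in days 7 to 90, the only period with both exposure states: 88 × 0.97 × (0.75 × 0.06 + 0.25 × 0.02) × 83/365 = 1.0.

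**The case against.** The strongest defence is that the grouping is deliberate. Protocol 10.6 pre-specifies on or off ACT/DAPT at discharge (or 30 days after implant) as a subgroup for secondary endpoints, and neither document calls the hazard ratio an on-treatment effect. That stands: dilution is an error only if the ratio is read as a therapy effect, and replacing the grouping by time-updated exposure would change the estimand. It does not cover events before discharge, which are misattributed even in a comparison by discharge status.

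A reader might infer that in-hospital events do decide discharge therapy, so that the ratio is bound to be diluted or reversed. The documents do not support this. The nearest text, in SAP 13.1.2, lists a change in medication regimen among the actions taken for an SAE. The rates of in-hospital bleeding and of discharge on therapy after a bleed are assumptions, and the same structure can inflate an effect or create one.

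Fewer in-hospital events than assumed may be captured. Enrolment dates from the later of consent and implant (Protocol 6.3.4), and Protocol 13.2 collects SAEs once a subject is enrolled, although Protocol 7.3 and 7.4 also list SAEs among the implant and discharge data. This could reduce the bias; nothing in the plan removes it.

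The remaining safeguards do not repair the model. SAP 13 tabulates SAEs by therapy period, but those tables do not feed the Cox fit. The Weibull fallback keeps the same covariate and origin and, with a common shape, is itself a proportional-hazards model.

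Finally, this is one covariate of twelve across eleven outcomes (132 single-covariate fits) in a study that Protocol 10 calls descriptive, and step 7 shows that no firm conclusion could come from it. That limits the importance of the point. It does not make the specification correct.

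**Conclusion.** The point holds as a minor one. From the documents alone, the ACT/DAPT covariate is set after time zero, pre-discharge events are attributed to a group not yet defined, and in-hospital deaths have no value.

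The size of the resulting bias depends on assumptions. If in-hospital events influence discharge therapy, the ratio may be reversed, inflated or spurious; if they do not, there is no reversal in the scenarios examined. Separately, with discharge at day 7 and stop at day 90, a true on-therapy ratio of 3 appears as about 1.5 (1.1 to 2.0 for stops at days 30 to 180) before any in-hospital event is counted. The ratio therefore cannot be reported as on-therapy versus off-therapy. The primary endpoint is unaffected.

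**What to change.** In SAP 11.5, for the ACT/DAPT covariate only:

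- Start the clock at hospital discharge (the discharge visit date already used in SAP 18.13), among subjects alive and free of the outcome being modelled at that point. This also settles how in-hospital deaths are handled.
- Label the result as association by discharge status, not as a therapy effect.
- Optionally, add a supplementary model with on/off exposure updated at ACTDIDAT and at recorded restarts, stating that it will rest on very few events (about one bleed in step 7). It should not replace the grouping defined in Protocol 10.6.
- Record the change in SAP 3.1, which at present reports no change in analysis from the protocol; Protocol 10.4 asks for this.

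The cost is SAP wording and one re-based dataset built from dates already collected. Pre-discharge events leave this one model, possibly about half of the bleeds (54% in step 7), so an already wide interval becomes wider. All other covariates and the Kaplan-Meier curves stay as they are.

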2. JUSTIFICATION FOR THE DESIGN OF THE CLINICAL INVESTIGATION

2.1. Introduction

Surgical aortic-valve replacement (SAVR) is the gold standard for the management of aortic valve stenosis. Recent innovations in therapeutic intervention, most notably transcatheter aortic valve replacement (TAVR), have been studied in several randomized clinical studies. The efficacy and safety of both treatment modalities are well established. Recently, findings of reduced leaflet motion in the Portico Resheathable Transcatheter Aortic Valve System U.S. Investigational Device Exemption (PORTICO IDE) study, the RESOLVE registry, and SAVORY registry have been reported in the literature. Further evaluation revealed that the reduced leaflet motion phenomenon is not isolated to TAVR devices. In fact, reduced leaflet motion was observed in subjects after both TAVR (10-40%) and SAVR (8-12%). with a bioprosthetic valve.

The Makkar et al report is the most comprehensive publication to date on reduced leaflet motion after AVR. Makker reported results from the PORTICO IDE study showing the overall incidence of reduced leaflet mobility to be 40% (22 of 55 subjects with evaluable 4D CT scans), 43% with Portico valves (16/37), 43% with Sapien XT valves (6/14), and 0% with CoreValve (0/9). Data from 132 subjects pooled from RESOLVE and SAVORY registries showed that the overall incidence was 13%; 14% after TAVR and 7% after SAVR. Among subjects with SAVR (27), the incidence was 9.1% (1/11) with Edwards Perimount, 11.1% with Perimount Magna (1/9); and 0% for the 6 subjects with Trifecta (3), Mitroflow (1), and Perceval (2) valves. Reduced motion was detectable by CT and transesophageal echocardiography with 100% concordance, but was undetected by transthoracic echocardiography, which is commonly used to evaluate bioprosthetic valve performance after implant. More importantly, the subjects were found to be hemodynamically stable at the time of detection, with aortic-valve gradients that were statistically similar to those with normal leaflet motion. The study also found that subjects on therapeutic anticoagulation had a lower rate of occurrence than among those receiving subtherapeutic or no anticoagulation. In addition, the authors reported that full or partial

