6.3.6. STUDY ENDPOINTS DEFINITIONS AND ASSESSMENTS

The primary endpoint will be evaluated with statistical hypothesis tests formally defined in Section 10.

Primary endpoint

The primary endpoint is the incidence of reduced leaflet motion identified through 4D volume-rendered CT imaging at minimum 1 month after the end of the anticoagulation or dual antiplatelet therapy (expected within 1 to 6 months post-implant, preferably 3 months), as assessed by an independent Core Lab. Enrolled subjects not receiving anticoagulation or antiplatelet therapy at discharge will be assessed via 4D volume-rendered CT imaging at a minimum of 30 days after hospital discharge.

• Secondary endpoints

The secondary endpoints are as follows:

- 1. Incidence of reduced leaflet motion (thrombus) with subanalysis in symptomatic and asymptomatic subjects, based on CT outcomes, and anticoagulation and dual antiplatelet treatment modalities, up to 1 year post-implant.
- 2. Incidence of reduced leaflet motion on 2nd 4D volume-rendered CT scan with contrast up to 1 year post-implant, in subjects in which reduced leaflet motion was previously detected.
- 3. Incidence and relationship of reduced leaflet motion to the device, procedure, or other causes up to 1 year post-implant.
- 4. Freedom from valve safety events (all-cause mortality, valve reintervention, myocardial infarction, structural valve deterioration, moderate or severe valve regurgitation, valve endocarditis, valve thrombosis, thromboembolic events, hemolysis and major bleeding) up to 1 year postimplant.
- 5. NYHA classification at 1 year post-implant.
- 6. Hemodynamic performance up to 1 year post-implant through TTE assessed by Echocardiographic Core Lab.

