7.7. UNSCHEDULED VISITS

Unscheduled visits in symptomatic subjects (subjects with symptoms of reduced leaflet function) and any other subjects needing a study related follow-up visit that is not covered by the standard visit schedule. The following items may be captured:

- Subject status
- Physical evaluation (including cardiac rhythm and NYHA functional classification)
- Medications
- Transthoracic echocardiogram (TTE) (if available)
- SAEs

7.8. 2ND CT SCAN VISIT/REDUCED LEAFLET VISIT (AFTER THE 1ST CT SCAN, BUT PRIOR TO 1-YEAR FOLLOW-UP VISIT)

This visit is intended provide a 2nd follow-up 4D CT scan if the 1st CT scan showed reduced leaflet motion. This second CT scan visit is expected at approximately 6-10 months, but prior to 1 year follow-up. This follow-up evaluation shall be conducted in an office, hospital or clinic setting by the PI or his/her designee, at a time designated by the PI.

If the 1st CT scan showed no signs of reduced leaflet motion, a repeat 4D CT is not mandated and will only be done if it becomes clinically indicated. For subjects unable to undergo a contrast CT scan (e.g. inadequate renal function), a TEE may be performed.

The following data listed below shall be collected if this visit is required:

- Subject status
- Physical evaluation (including cardiac rhythm and NYHA functional classification)
- Medications

- Hemodynamic data from TTE examination measured at investigational site (MPG; PPG, EOA, aortic regurgitation with severity and location)
- CT scan with contrast
- TEE only in subjects that are unable to undergo CT scan at the time of follow-up
- Medications
- SAEs

7.9. 1-YEAR FOLLOW-UP VISIT

This visit is intended as a clinic visit at 1 year \pm 1 month after the day of the surgery. Follow-up evaluations shall be conducted in an office, hospital or clinic setting and are to be performed by the PI or his/her designee. **All efforts should be made to ensure that the subject comes to the clinic.**

The following data listed below shall be collected:

- Subject status
- Physical evaluation (including cardiac rhythm and NYHA functional classification)
- Medications
- Hemodynamic data from TTE examination measured at investigational site (MPG; PPG, EOA, aortic regurgitation with severity and location)
- Medications
- SAEs

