7.11. BLINDING OF CT IMAGING RESULTS

Blinding of CT imaging results, for the purpose of evaluation of reduced leaflet motion, has been implemented to minimize the PI's exposure to imaging information that would typically not be obtained through standard of care practices. This blinding is intended to

prevent influence of the subject's (medical) treatment based on the possible findings of the CT scan.

To limit access and visibility of the CT images they will be sent directly to the Core Lab, which will be responsible for the assessment. Core Lab findings will not be sent to the site or accessible to sites in the EDC system. If, through assessment of the CT scan, the Core Lab becomes aware of findings that would potentially jeopardize subject safety (i.e. thrombus), the PI will be notified. Any medical circumstance requiring the PI's access to the CT scan or imaging results will lead to unblinding of the PI, possible unblinding of the subject, and may result in an adjustment of the subject's treatment (including medication) based on the PIs discretion.

For asymptomatic subjects, PIs and subjects will be blinded from the CT imaging results and from the Core Lab findings. Investigators will be requested to not alter relevant antiplatelet or anticoagulation drug therapies for asymptomatic subjects. The need for and use of antiplatelet or anticoagulation drug therapy will be assessed at each follow-up visit.

Symptomatic subjects and the PI can be unblinded to CT imaging results based on any treatment deemed necessary by the PI or treating physician. In this case, the PI can request CT scan results from the Core Lab as they will not be automatically sent to the site. Symptomatic subjects are those with clinical symptoms, such as, but not limited to shortness of breath, fatigue, or signs of thromboembolic events, as assessed by the treating physician. Asymptomatic subjects with reduced leaflet mobility on their 1st CT scan, and who have an increase in valve gradients, may be unblinded. This determination will be made by the Core Lab and/or Coordinating Investigators, and revealed to the study site through the LivaNova Project Manager or designee.

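### The hazard ratio of reduced leaflet motion at first CT for valve thrombosis is open to detection bias: the same scan can trigger the thrombosis report, and only positives must be rescanned

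*SAP*

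**What the plan says.** SAP 11.5 names eleven mortality and morbidity outcomes for time-to-event analysis, including valve thrombosis. It then enters a list of covariates into Cox models one at a time. One of them is "reduced leaflet motion at first CT scan [refers to 'No", with No as the reference level. No outcome is exempted. SAP 18.13 computes time to event as "Even date – DXSTDAT2 + 1] / 30.4375", that is, in months from the implant date.

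Four places in the protocol bear on how the covariate and this outcome are related:

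- Section 6.3.6 words the first secondary endpoint as "Incidence of reduced leaflet motion (thrombus) with subanalysis in symptomatic and asymptomatic subjects". Section 2.1 gives leaflet thrombosis as the hypothesised cause of reduced motion.
- Section 7.11 says that if the Core Lab's reading of the CT reveals "findings that would potentially jeopardize subject safety (i.e. thrombus), the PI will be notified". Section 12.1 requires the investigator to report serious adverse events and lists valve thrombosis among them. Section 13.3 has the Clinical Events Committee adjudicate it.
- Table 2 in section 8.1 schedules the second CT for subjects with reduced motion on the first. For the others, section 7.8 says "a repeat 4D CT is not mandated and will only be done if it becomes clinically indicated".
- All subjects have transthoracic echocardiography at the first-CT and 1-year visits. Section 2.1 reports that in the earlier work reduced motion was seen on CT and transesophageal echo "but was undetected by transthoracic echocardiography".

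Neither document says whether thrombosis found only on a study scan counts as an event in this model.

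**The concern.** Two mechanisms can link the covariate to the outcome without any clinical effect of reduced motion.

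1. **Shared ascertainment.** One CT reading can set the covariate to Yes and also start the chain that ends in a thrombosis record.
2. **Differential detection.** After the first scan, positives have a required second CT and further routes to unblinding (protocol 7.11). Negatives are rescanned only on clinical grounds, so clinically silent thrombus is less likely to be found in them.

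Whether subclinical reduced motion carries clinical risk is a question that the protocol's introduction raises. A large hazard ratio for valve thrombosis could be read as an answer to it when it reflects only how cases were found.

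**Working it through.** **The plan's own figures.** The documents give no hazard ratio, event count or power for the Cox models. The only related figures are those for sample size, and they reproduce. The exact 90% interval at 7/75 (9.3%) is about 12.4 points wide and at 10% about 12.7, both under 13. Also 75/0.85 = 88.2, about 88 enrolled.

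**Inputs from the documents.** 75 evaluable scans; planning proportion below 10% (protocol 10.2), with 8-12% quoted for surgical valves (2.1). No valve thrombosis in 756 pooled subjects (2.3.1), for which the exact one-sided 95% upper bound is 1 - 0.05^(1/756) = 0.40%. Second CT on days 180-300 and at least 6 weeks after the first (7.10).

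**Assumptions, not in the documents.** The true hazard ratio for clinically arising thrombosis is 1. Background hazard λ is 0-3% per year. A share q1 of positives has thrombosis recorded because of the first CT, and a share q2 of the remaining positives because of the second. The first CT falls on days 60-180.

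**Step 1: expected size.** Over one year the cumulative hazard is λ in negatives and λ - ln[(1-q1)(1-q2)] in positives. The ratio is

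HR ≈ 1 - ln[(1-q1)(1-q2)]/λ.

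For q1 = 10%, q2 = 0 and λ = 0.01 this is 1 + 0.1054/0.01 = 11.5. A simulation of the Cox model as specified (time from implant, 10% positive, 400,000 subjects) agrees:

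| q1, q2 | λ = 1%: formula / simulated | λ = 3%: formula / simulated |
|---|---|---|
| 0, 0 | 1.0 / 1.03 | 1.0 / 1.04 |
| 10%, 0 | 11.5 / 11.4 | 4.5 / 4.6 |
| 25%, 10% | 40.3 / 40.8 | 14.1 / 14.1 |
| 50%, 25% | 99.1 / 97.8 | 33.7 / 34.0 |

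If 2% of negatives also have a scan-triggered record (q1 = 25%, q2 = 10%), the simulated ratio is 8-15 for λ from 3% down to 0.5%.

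**Step 2: at the planned size.** With 75 subjects, 10% positive, q1 = 25% and q2 = 10%, a positive has a scan-triggered record with probability 1 - 0.75 × 0.90 = 0.325. The expected number is 75 × 0.10 × 0.325 = 2.4. With no background events every case is a positive, and the hazard ratio is infinite whenever there is at least one: 1 - (1 - 0.0325)^75 = 0.92. In 4,000 simulated trials 92% were infinite and 8% had no event. With λ = 1%, 46% were infinite and the median finite ratio was 21. Mean event counts for this q1 and q2 were 2.4-4.7 for λ from 0 to 3%. For comparison, 80% power at two-sided 10% with one subject in ten exposed needs 13 events for a true ratio of 10.

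**Step 3: which change removes the bias.** Starting the clock at the first CT is not enough by itself: where the second CT also triggers records, the simulated ratio stays at 6-84. With the later start and scan-triggered cases excluded, it returns to about 1 (0.89-1.19 over the scenarios run, which is simulation noise).

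**The case against.** The strongest reply is that valve thrombosis is not a CT reading. It is an investigator-reported serious adverse event, adjudicated by an independent committee under protocol definitions. Those definitions belong to Appendix 1, whose text is not in the supplied file, and a strictly clinical definition would narrow the problem. Core Lab findings do not go routinely to sites, and the notice in protocol 7.11 is for findings that may endanger the subject. Only serious events are recorded, and an incidental image need not qualify.

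This reply stands against three stronger readings that a reader might infer:

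- *Covariate and outcome both come from the same scan.* The documents show that they can. Thrombosis may also come to light through symptoms, unscheduled visits or transthoracic echo.
- *Only positives get another CT.* Only positives are required to have one. Negatives may have one if clinically indicated, and SAP Table 3 provides for No followed by Yes.
- *A large hazard ratio arises by construction.* It does not: with no scan-triggered cases the simulated ratio is about 1. Treatment changes after unblinding could also lower it. The reference group can have scan-triggered cases too, because every first CT is read and SAP 10.3 counts mildly reduced motion as no reduction.

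The second-CT route alone is also weak at this size. If silent thrombus occurred in an assumed 3% of 6-9 positives, 0.18-0.27 cases would be expected, and the chance of even one would be 17-24%.

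Finally, protocol section 10 calls the study descriptive and non-confirmative, and this is one covariate for one of eleven outcomes. That limits the consequence. It does not answer the gap: the plan fits the model without saying how scan-triggered thrombosis is counted.

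**Conclusion.** The concern holds as a risk of shared-ascertainment and differential-detection bias. Counting scan-triggered cases that arise mainly in positives pushes the hazard ratio upward. With few background events it could be large or inestimable although reduced motion has no clinical association with thrombosis.

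Only the direction is firm. The illustrative values (about 11 when 10% of positives are scan-triggered at 1% background per year, 4.6 at 3%, about 1 with none) rest on assumed shares and on a definition of valve thrombosis that the supplied text does not show. The primary incidence estimate is untouched. This is a cheap improvement to a secondary, descriptive analysis.

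**What to change.** In SAP 11.5, omit reduced leaflet motion at first CT as a covariate for the valve thrombosis outcome. List thrombosis cases descriptively by first-CT result and by route of detection: study CT or TEE, symptoms, gradient rise, embolism or re-intervention. This needs one line in the SAP and one detection flag on the adjudicated event, and it costs one hazard ratio that few events would support anyway.

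Alternatively, keep the model but restrict it to thrombosis diagnosed independently of a study CT or TEE, start time at the first CT, and list image-detected cases separately. Both the restriction and the later start belong together here. The cost is fewer countable events.
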